3. HUMAN SUBJECTS

3.1 SUBJECT POPULATION

The anticipated age range for the study population will be ≥ 70 years of age based upon the target disease population. Thirty subjects with any ethnic background who have a confirmed diagnosis of HFrEF/HFpEF/healthy control will be eligible for enrollment. All subjects must provide written informed consent prior to participation.

3.1.1 Inclusion of Women and Minority

Women who meet the inclusion criteria, and have none of the exclusion criteria, will be enrolled without restriction as dictated by the study protocols. We will make efforts to enroll participants in this research in a distribution that mirrors the study population of the Pittsburgh area.

3.1.2 Inclusion of Children

This investigation will not enroll children based upon the target disease population and lack of safety data in adults.

3.2 INCLUSION CRITERIA

Inclusion Criteria HF Population

- NYHA class II or III for the previous three months despite a minimum of 6 weeks of treatment. Echo criteria will be confirmed as part of the initial study assessment.
- Age ≥ 70 years
- HFrEF patients left ventricular ejection fraction [LVEF] $< 40\%$
- HFpEF patients LVEF $\geq 40\%$, may also include E/E' > 8 , left atrial size > 40 mL/m²
- Optimal therapy according to AHA/ACC and HFSA HFrEF guidelines, including treatment with ACEI and beta-blocker therapy (for at least 6 weeks), or have documented reason for variation, including medication intolerance, contraindication, patient preference, or personal physician's judgment.
- Patients using aspirin (ASA) will be eligible, but asked to hold the medication for 48 hours prior to biopsy. This technique has previously been used with consistent safety. Patients will also be asked to avoid non-steroidal anti-inflammatory medications (NSAIDs) for 48 hours prior to the biopsy.
- Patients using anti-thrombin and anti-platelet therapy will plan to modify prior to muscle biopsies individually in coordination with the participant's primary care provider or cardiologist.
- Baseline BP $\leq 170/95$: subjects with either systolic or diastolic over stated level are ineligible.
- Subjects who report using PDE-5s will be asked to hold the medication 24 hours before initial nitrite dose and for the entire period on study drug.

Inclusion Criteria Age-Matched Control Population

- Age ≥ 70 years
- Absence of clinically significant chronic disease processes (including cardiovascular disease, diabetes, cancer, CKD, liver disease, COPD, and/or osteoarthritis). Non-significant cardiac rhythm abnormalities and stable hypertension are acceptable for inclusion.
- baseline BP $\leq 170/95$: subjects with either systolic or diastolic over stated level are ineligible.
- Patients using aspirin (ASA) or NSAIDs will be eligible, but asked to hold the medication for 48 hours prior to biopsy. This technique has previously been used with consistent safety. Patients

will also be asked to avoid non-steroidal anti-inflammatory medications (NSAIDs) for 48 hours prior to the biopsy.

- Patients using anti-thrombin and anti-platelet therapy will hold these medications prior to muscle biopsies in coordination with each subject's primary care provider or cardiologist.
- Subjects who report using PDE-5s will be asked to hold the medication 24 hours before initial nitrite dose and for the entire period on study drug.

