2.2.5. Medication Compliance

Subjects will self-administer their first dose of study medication under the supervision of the CTRC nurse (physician investigator will be immediately available) in the outpatient CTRC during Visit 3, following completion of all baseline clinic assessments. Subjects will also be dispensed their study medication (42-day supply) for home use, including four 7-day prefilled and labelled pill boxes and drug/symptom diary cards to help with compliance and to help reduce burden or confusion. (Visit 4 may be scheduled up to and on the 42nd day from visit 3 (25-35±5 days); additional drug will be distributed with the initial dispensation if needed to meet the need.) Subjects will return the previously dispensed study medication when they return for Visit 4 approximately 4 weeks later (+1 week if need be for flexibility of scheduling) and medication compliance will be assessed. The study coordinator will review the daily diary card with each phone call evaluation and also assess medication compliance with queries regarding empty pill compartments in the current 7-day box and remaining boxes. In the event that the compliance rate is <80% (subjects' report of doses taken/total doses prescribed at that date & time *100), subjects will be re-educated on medication compliance. If medication compliance repeatedly falls outside of the acceptable range, the study investigators will discuss subject eligibility for continued participation in the study.

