Subjects who fail to meet applicable inclusion/exclusion criteria based upon the results of the screening assessment will be excluded from further study participation.

An important component of the protocol is the muscle biopsy. Subjects who refuse the first biopsy will be excluded at screening. Participants who undergo the first biopsy at Visit 3 may refuse a second pass. (Participants may also refuse a second biopsy pass at Visit 5). However, participants who refuse to complete a second biopsy at Visit 5 (prior to starting sodium nitrite) will be withdrawn from the study. Alternatively, patients who refuse the 2nd biopsy after they have completed the 4 weeks of nitrite therapy will still be included.

Visit 2 (First Baseline Assessment Visit)

Subjects will be scheduled for an outpatient EMRC and Pepper SMART Center visit within 4 weeks of screening. The subject will be asked to refrain from caffeine the morning of this visit and to limit breakfast to a lighter meal prior to coming in. The visit will last approximately 3 hours.

Interval history and brief physical exam: temperature, blood pressure, pulse oximetry, breathing rate, heart rate and body weight

Physical Function Battery:

- Cardiopulmonary Stress Exercise Testing: Exercise testing in association with air-gas-exchange, an optimal gauge of aerobic capacity will be conducted by trained research exercise

physiologists. [name] or another physician will be immediately available if needed. A computerized cycle ergometer using a ramp protocol will be used to generate a symptom limited exercise stimulus. A lightweight disposable pneumotach device face mask will be positioned over the subject's mouth and nose during the exercise for gas exchange assessments of VO_2 , VE/VCO_2 slope, and respiratory exchange ratio (RER) will be measured as well as hemodynamics (max heart rate [HR] and blood pressure [BP]), time, and ECG waveforms). Any unexpected abnormalities will be reported to a patient's cardiologist or primary care physician; continued participation in the study will require physician clearance. Both the Borg Rate of Perceived Exertion (RPE) and the Modified Borg Scale for Perceived Dyspnea (Shortness of Breath) will be completed during the CPX. The EMRC has performed similar tests in more than 1,000 volunteers ranging from elderly women in their 80's to highly trained athletes.

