This visit involves a percutaneous muscle biopsy, blood draw, first dose of study medication and dispensing of study medication. To prevent acute effects of exercise on muscle mitochondria function, this fasting visit will occur 2-7 days after Visit 2. This visit will take place at the MUH-CTRC and will last 4-5 hours. Subjects will be asked to observe 8 hours fasting prior to arrival. Upon arrival subjects will be weighed and then served a standardized breakfast [15% of 30 calories/kg current body weight (CBW) and 15% of 1.0 gm protein/kg CBW, low nitrite/nitrate] in

the CTRC. A dietitian will review and adjust subjects' food choices as needed to meet the standardized diet prescription.

Interval history and brief physical exam: temperature, blood pressure, pulse oximetry, breathing rate, heart rate and body weight. Blood pressures may be re-measured to allow for clinical variation. Prior to the biopsy, study staff will call indicated subjects to hold their anti-platelet and anti-coagulation medications for 1-5 days (depending on the different medications and relative half-lives). In each instance a subject is on an anti-platelet or anti-coagulation medication, the plan to hold the medication prior to the biopsy will first be cleared by the study physician with the subject's own primary care provider or cardiologist. Physician orders for CTRC will include confirmation with subject upon arrival.

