Subjects will rest for approximately 30 minutes post biopsy while wound is dressed and prior to baseline vitals prior to dosing. Study staff will record a baseline level of symptoms, including shortness of breath, dizziness, lightheadedness for use during weekly phone calls, prior to dosing.

Following biopsy, subjects will receive their first dose of study drug as follows:

- 14N sodium nitrite, 20 or 40 mg per physician order
- Blood pressure (sitting and then standing after 3 minutes), HR, RR, pulse oximeter and methemoglobin will be measured to ensure they are at a steady state before taking the study drug (baseline) and then approximately every 15 minutes for the 2 hours post-drug administration. Any perturbations of concern will be addressed per the Dose Reduction protocol described in Section 2.2.6.
- AE assessment
- Provide a 42-day supply of study drug, pre-filled in 4 weekly pill boxes and an extra bottle and drug diary cards to assist with compliance and reduce burden or confusion. Study staff will review medication administration and use of the drug diary card with all subjects. Study staff or CTCR RN will review biopsy site care with subjects and if indicated, remind subjects to resume their normal anti-coagulation and anti-platelet medications the following day (as indicated).
- 24-hour dietary recall. The study coordinator will collect a second 24-recall of all foods eaten from subjects for analysis for calories, macronutrients, sodium, nitrates and nitrites.

Subjects will be reminded before departure to report promptly any changes in their medication, health or symptoms of concern, not to wait for the weekly call.

Visit 4 (First Completion Assessment visit to be scheduled 25-35±7 days following first dosing of 20-40 mg oral nitrite) Subjects who need more than 42 days' supply of drug due to scheduling later in window will be issued additional at visit 3.

This visit will take place in the EMRC and/or Pepper SMART Center and is identical to visit 2 (approximately 3 hours):

Interval history and brief physical exam: temperature, blood pressure, pulse oximetry for methemoglobin %, breathing rate, heart rate and body weight; additionally, AE and symptom assessment will be collected and medication compliance via drug diary cards and pill boxes will be assessed.

Physical Function Battery:

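### As written, the PDE-5 hold starts after the Visit 2 function tests and covers Visit 4, so for anyone taking the drug around Visit 2 the functional change mixes starting nitrite with stopping it

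*Combined protocol and SAP*

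**What the plan says.** PDE-5 inhibitor users are eligible in every group. Section 3.2 states the same rule for heart failure patients and for controls, and the synopsis repeats it: those who report use are asked to "hold the medication 24 hours before initial nitrite dose and for the entire period on study drug".

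The first nitrite dose is taken "during Visit 3, following completion of all baseline clinic assessments" (section 2.2.5). The physical function tests and quality-of-life questionnaire belong to Visit 2 (section 2.3.1 and Table 1). Section 2.3.1 then says of Visit 3 that "this fasting visit will occur 2-7 days after Visit 2". The preparation rules for Visit 2 concern caffeine ("The subject will be asked to refrain from caffeine the morning of this visit") and a light breakfast. They do not mention PDE-5 inhibitors.

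Visit 4 is the "First Completion Assessment visit to be scheduled 25-35" days after the first dose, with a window of 7 days either way. Of its content the protocol says "This visit will take place in the EMRC and/or Pepper SMART Center and is identical to visit 2". Study drug continues until the morning of Visit 5.

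The model in section 2.5 has fixed effects for group, time point and their interaction, and a random effect for participant. It has no term for concomitant medication. Under section 2.1 the study is open-label and non-randomized, and all three groups receive nitrite.

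**The concern.** The evidence on function is a before-and-after comparison with no untreated arm. Such a comparison credits nitrite with everything that changes between the two time points, so a co-medication should be in the same state at both. Here a rule in the protocol, followed exactly, allows the PDE-5 state to differ: usual use is permitted up to and including Visit 2 and withheld at Visit 4.

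The measures at stake are those under Aim 5 (clinical indices) and Aim 6 (oxygen uptake at the same work intensity). Comparing changes between groups removes the problem only if PDE-5 use is similar across the groups. Nothing in a non-randomized design ensures that. Section 2.5 also relies on plots of individual participants, on correlations between changes, and on descriptive statistics for sizing a later trial. At this sample size, one or two affected subjects can be visible in all of these.

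**Working it through.** **Timing.** Count days from Visit 2 as day 0.

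- Visit 3 and the first dose fall on day 2 to day 7 (section 2.3.1, Table 1).
- The hold starts 24 hours before that dose, on day 2 − 1 = 1 to day 7 − 1 = 6.
- The gap from the Visit 2 battery to the start of the hold is therefore about 1 to 6 days. It is positive on every permitted schedule.
- Visit 4 is 25 to 35 days after the first dose, so 25 + 1 = 26 to 35 + 1 = 36 days into the hold. With the 7-day window this becomes 18 + 1 = 19 to 42 + 1 = 43 days. Section 2.2.5 prints a 5-day window instead, which gives 21 to 41 days and the same conclusion.
- Study drug runs to the morning of Visit 5, so Visit 4 always lies inside the hold.

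**Biopsy and blood endpoints.** The pre-dose samples at Visit 3 are taken a little under 24 hours into the hold. Visit 5 is nominally 2 to 7 days after Visit 4, so 26 + 2 = 28 to 36 + 7 = 43 days into it. Both visits are at or within the hold. The contrast is about a day off the drug against several weeks, a weaker form of the same mismatch.

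**Correlations.** In an affected subject, the muscle change (Visit 3 to Visit 5) lies almost wholly within the hold, while the function change (Visit 2 to Visit 4) spans its start. The two changes that section 2.5 correlates then reflect different PDE-5 contrasts.

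**The plan's own figure, for scale.** Section 2.5 gives an SD of 32 pmol O₂/min/10⁶ cells for the change in platelet respiration, and detectable differences of 32 within a group and 42 between groups at 80% power, two-sided 0.05. No per-group split is stated. With an assumed 10 per group, a noncentral t calculation gives 31.9 within a group (power at 32 = 80.3%) and 42.4 between groups (power at 42 = 79.3%). The plan's figures are reproduced and are not in dispute. The detectable within-group change is 32/32 = 1.0 SD. No SD is given for the function measures, so this serves only as a yardstick.

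**Shift in a group mean.** With k users among 10 and a withdrawal effect w, in SD units of the change:

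shift = k × w / 10

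The documents give neither k nor w. The values below are assumptions chosen to show a range, with w from 0.25 to 1 SD.

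| k | shift at w = 0.25 | shift at w = 1 |
|---|---|---|
| 0 | 0 | 0 |
| 1 | 0.025 SD | 0.10 SD |
| 3 | 0.075 SD | 0.30 SD |
| 5 | 0.125 SD | 0.50 SD |

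**The case against.** A reader might infer that every PDE-5 user is tested on the drug at baseline and off it at Visit 4, and that the functional results are therefore biased. The documents do not support that. They refer to subjects who report use, without frequency, dose or indication. Use at Visit 2 is permitted but not established, and an occasional user may have taken none near that visit. Nor do the documents describe any effect of PDE-5 inhibitors, or of stopping them, on exercise, walking, strength or quality of life. Size and direction are both unknown.

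Three further objections carry weight.

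- **Size.** Under the assumed range, one user moves a group mean by at most 0.10 SD, against a detectable change of 1.0 SD. Reaching 0.50 SD takes five users in ten, each with a 1 SD effect, and nothing in the documents suggests this.
- **Scope.** The only endpoint used for sizing, platelet respiration, is measured at Visits 3 and 5, and Aims 1 to 4 are largely outside the point.
- **Consistency of the rule.** The hold is stated alike wherever it appears and is tied to the nitrite dose. Aligning it with Visit 2 would in practice be a clinical decision, which is not for a statistical review to make.

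It can also be said that interval histories and plots of individual data would reveal a discordant subject. That is only partly so. Table 1 provides for an interval history at Visits 2 to 5, but nothing requires PDE-5 use or last intake to be recorded at Visits 2 and 4, and section 2.5 does not say what would be done with the information.

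**Conclusion.** The timing mismatch is certain on the documents: it holds in every allowed visit window, and no section starts the hold earlier. Its consequence is conditional. For a subject actually taking a PDE-5 inhibitor around Visit 2, the Visit 2 to Visit 4 change combines starting nitrite with stopping the other drug, and the planned model cannot separate them. For everyone else there is no effect.

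The shift in a group's mean change is k × w/10, assuming 10 per group. It is zero without users, modest with one or two, and of unknown sign. The point concerns mainly the function and quality-of-life measures. It does not call the trial's other endpoints or its sample size into question. It merits a change because the remedy in the analysis costs almost nothing and use at Visit 2 that was never recorded cannot be reliably reconstructed later.

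**What to change.** 1. At Visits 2 and 4, record whether the subject uses a PDE-5 inhibitor and when it was last taken.
2. In section 2.5, prespecify that all Visit 2 to Visit 4 changes, and the correlations that use them, are reported with and without subjects using a PDE-5 inhibitor at Visit 2. State how many such subjects there are in each group.
3. The investigators should reconcile the hold wording in section 3.2 and the synopsis with the visit schedule. No start or length of hold is proposed here. If they change the rule, earlier and later enrollees will have different baseline conditions, and the report should say so.

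The cost is two items on a form, one sentence in section 2.5 and a smaller sample in one sensitivity analysis. On the plan's platelet yardstick, going from 10 to 9 subjects in a group raises the detectable within-group change from 31.9 to 34.1 (34.1/32 = 1.07 SD). Going to 8 raises it to 37.0 (37.0/32 = 1.16 SD). The 10 controls and three heart failure subjects that section 2.2.2 reports as already enrolled can be flagged only from existing medication history.

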2. RESEARCH DESIGN AND METHODS

2.1 CLASSIFICATION AND METHODOLOGICAL DESIGNS

The study is a 4-week open-label, single-center, non-randomized drug treatment study of 3 groups: HFpEF, HFrEF, healthy age-matched controls.

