Nine of 10 control subject enrollees into this pilot study have tolerated 40 mg po tid without incident; the one exception was a subject who had a decrease in systolic BP at pK but was asymptomatic. In the three heart failure subjects enrolled to date we have observed a vasoactive response at the pK with the 40 mg dose, such that low blood pressures or symptoms have been observed in the 2 hour monitoring period. This includes subjects with preserved and reduced ejection fraction. Therefore, we postulate the heart failure subjects appear to have a greater vasodilatory response to nitrite and could require a stratified dose based on age and baseline risk for hypotension. To further ameliorate risk, we will serve a standardized meal prior to drug dosing at Visit 3 so that lack of po intake is not a causative factor of hypotension.

In summary, based on the above findings, inclusive of:

- The Joint FAO/WHO ADI for sodium nitrate and nitrite,
- the above DASH diet patterns,
- the recently observed human and rodent effects of nitrate and nitrite on blood pressure and glucose homeostasis, including our PK/PD trial of single doses of oral nitrate and nitrite,
- the open label trial safety and BP findings following a total of 10 subjects' completion,
- the existing inhaled nitrite trial,
- the preliminary findings of the current nitrite protocol with regard to blood pressure in heart failure subjects,

the study investigators believe that a safe and likely therapeutically effective dose of sodium nitrite will be 20-40 mg three times daily (~0.21-0.42 mg/kg body weight per day for a 95 kg subject). The 40 mg sodium nitrite dose selection is equivalent to 12.6 times the ADI.

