Data Analysis: Our analytic strategy will involve formal statistical analyses, but in our interpretation, we will also pay attention to descriptive statistics, graphical summarizations of individual participant data such as needle plots (51,52), and magnitudes of parameter estimates from modeling in addition to their statistical significance based on *p*-values and a strict criterion based on $\alpha=0.05$. Such an interpretive strategy is appropriate in an initial study such as ours, where the cost of a missed finding is far greater than a false finding. We will fit a series of linear mixed models using the SAS[®] MIXED procedure (SAS Institute, Inc., Cary, North Carolina) with each of the skeletal muscle, platelet, gene expression, inflammatory, oxygen uptake and physical function related measures as the dependent variable; participant group (HF_rEF/HF_pEF/control), time point (baseline/4-week) and their interaction as fixed effects of interest; and a participant random effect to account for multiple measurements from the same participants. We will appropriately create means contrasts to estimate (a) between time changes in each of the groups corresponding to periods of usual care and nitrite usage, and (b) compare the said changes across the three groups. We will use Pearson/Spearman correlations to quantify strength of associations between changes in measures of skeletal physiology and those of strength, gait speed and balance. Finally, in addition to drawing preliminary conclusions, we will use our descriptive statistics for formal sample size computations in planning a larger subsequent trial to more definitively examine the impact of nitrites.

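### The controls are called age-matched, but all groups share only an age floor of 70, and neither recruitment nor the model for the between-group contrast deals with age

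*Combined protocol and SAP*

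**What the plan says.** Section 2.1 describes a "non-randomized drug treatment study of 3 groups: HFpEF, HFrEF, healthy age-matched controls". The age-matched label also appears in the synopsis (Study Rationale and Major Inclusion Criteria), in section 2.2.3 and in section 3.2, where the control criteria are headed "Inclusion Criteria Age-Matched Control Population".

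The age criterion under that heading is 70 years or older, the same line that HF subjects must meet. Section 3.1 confirms that there is no upper limit: "The anticipated age range for the study population will be ≥ 70 years of age based upon the target disease population". The recruitment methods in section 4.1 mention no pairing, age band, quota or caliper.

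On enrolment so far, section 2.2.2 reports "Nine of 10 control subject enrollees into this pilot study have tolerated 40 mg po tid without incident" and "In the three heart failure subjects enrolled to date we have observed a vasoactive response". The synopsis (Study Design) assigns dose partly by age, with a cut at 80 years.

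Section 2.5 fits linear mixed models with participant group, "time point (baseline/4-week) and their interaction as fixed effects of interest", plus a participant random effect. Contrast (a) estimates the change within each group. Contrast (b) is to "compare the said changes across the three groups". No age term is named.

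**The concern.** In a non-randomized study, comparability between groups has to come from selection or from adjustment. A shared floor of 70 restricts the age range but does not match: a control group averaging 72 and an HF group averaging 83 would both comply. The plan thus claims a design property that eligibility does not deliver and the analysis does not replace.

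Contrast (b) is at stake. If the groups differ in age and age affects how subjects respond to nitrite, a difference in change between HF subjects and controls mixes disease with age. Age can also enter through dose, because older subjects are assigned differently. The report could then defend the contrast as age-matched when nothing made it so, and section 2.5 intends to use the results to plan a larger trial.

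**Working it through.** **1. Group sizes implied by the plan.** The 30 subjects are not split by group in the documents. Section 2.5 gives an SD of change of 32 pmol O2/min/10^6 cells and detectable differences of 32 (within group) and 42 (between groups) at 80% power, two-sided 0.05. Assuming 10 per group and using the noncentral t:

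- Within group (one-sample t, 9 df): detectable change 31.9; power at 32 is 80.3%.
- Between groups (two-sample t, 18 df): detectable difference 42.4; power at 42 is 79.3%. With error pooled over three groups (27 df), it is 41.6.

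The plan's figures reproduce at 10 per group, and the age point changes neither. On that reading the 10 controls enrolled are the whole control group, while 20 − 3 = 17 HF subjects were still to come.

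**2. What can bias contrast (b).** For a subject in group g with age A, write baseline = level_g + γA and change = δ_g + βA, with A measured from a common reference age. The term γA is present at both time points and drops out of the change. The expected contrast is then

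(δ_HF − δ_control) + β × (mean age in HF − mean age in controls).

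Bias needs both an age gap and a non-zero β, meaning that age modifies the four-week response. Contrast (a) estimates each group's own mean change and needs no matching.

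**3. The dose route.** If the two dose levels produce different changes, contrast (b) also picks up that difference multiplied by the gap between groups in the proportion on the higher dose. The early enrollees in section 2.2.2, controls and HF alike, are described at 40 mg. Later HF subjects are assigned by age and hypotension risk under the synopsis rule. Group, age and dose can therefore be entangled. The documents give no figures from which to size this.

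**4. Illustrative size.** The documents give neither ages by group nor a slope of change on age; both are assumed here. Bias in SD = age gap × slope; bias in pmol = that × 32. The false-positive rate is for a nominal 5% two-sided test, 10 v 10, 18 df, noncentrality = bias in SD / √(2/10).

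| Age gap (years) | Slope (SD/year) | Bias (SD) | Bias (pmol) | False-positive rate |
|---|---|---|---|---|
| 3 | 0.02 | 0.06 | 1.9 | 5.2% |
| 3 | 0.05 | 0.15 | 4.8 | 6.2% |
| 3 | 0.10 | 0.30 | 9.6 | 9.7% |
| 5 | 0.02 | 0.10 | 3.2 | 5.5% |
| 5 | 0.05 | 0.25 | 8.0 | 8.3% |
| 5 | 0.10 | 0.50 | 16.0 | 18.5% |
| 8 | 0.02 | 0.16 | 5.1 | 6.3% |
| 8 | 0.05 | 0.40 | 12.8 | 13.5% |
| 8 | 0.10 | 0.80 | 25.6 | 39.5% |

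A different pair of assumptions, an age–change correlation of 0.2 to 0.4 and a gap of 0.5 to 1 SD of age, gives 0.1 to 0.4 SD, or 3.2 to 12.8 pmol. The results run from negligible to serious, which shows that the documents do not fix the size.

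**The case against.** The strongest reply has four parts.

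- **The label may mean only that every group has the same age restriction.** The synopsis rationale introduces all three groups as adults aged 70 or older, and the criterion is openly identical, so nobody is misled about eligibility. That stands for eligibility. For a between-group comparison, the term still promises more than a common floor.
- **The rationale's statements about age concern levels of function, and contrast (b) compares changes.** This stands. A stable age effect on level cancels, so those statements do not by themselves show bias.
- **The contrast is secondary in a pilot.** None of the six aims states a difference between HF and controls, and section 2.5 regards a missed finding as costlier than a false one. This limits the severity. It does not excuse the label, because formal tests at 0.05 across groups are planned.
- **Age adjustment at n = 30 is hard to interpret.** Age is tied to dose and possibly to group, and HF subjects differ from controls by design in comorbidity and medication. This stands, and it is why an adjusted estimate belongs beside the unadjusted one and should not replace it.

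**Conclusion.** The point holds as a mismatch between a stated design property and what the plan does. The age-matched label is backed by no matching procedure and no age term, so contrast (b) can be confounded if age modifies the response to nitrite or acts through dose assignment. Within-group changes are untouched by the lack of matching. It is worth correcting because the correction is cheap, but it does not threaten the study's stated aims.

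Three stronger statements that a reader might infer are not supported:

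- **That the controls are younger than the HF subjects.** The controls' comorbidity exclusions make this plausible, but HF subjects are also filtered (NYHA II or III, no dementia, no orthopedic exercise limitation, willing to undergo biopsy), and no ages are reported.
- **That 10 controls against three HF subjects makes matching impossible.** This is an interim count, and the 10-per-group split is inferred. Later HF subjects could still be recruited to the controls' age distribution; the gap is that no rule requires it.
- **That the bias has a known size.** The figures above follow from assumed gaps and slopes and are illustrative only.

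**What to change.** 1. **Wording.** Replace age-matched with aged 70 years or older in all five places: synopsis Study Rationale, synopsis Major Inclusion Criteria, and sections 2.1, 2.2.3 and 3.2. Changing only some would create a new inconsistency. Keep the label only if the remaining HF subjects, in each HF group, are frequency-matched to the enrolled controls by age band, with the rule written into section 4.1. The bands 70 to under 80 and 80 or older are already used in the protocol.
2. **Reporting.** Tabulate age and assigned dose by group.
3. **Analysis.** In section 2.5, for contrast (b), report beside the unadjusted estimate one from a model that adds centred baseline age and age-by-time. State that it does not remove differences in dose, comorbidity or medication between HF subjects and controls.

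Age is already known from eligibility, so no new data are needed. The model change costs one or two degrees of freedom: at 10 per group, the error df for the change contrast falls from 30 − 3 = 27 to 30 − 4 = 26, and the age main effect uses one more between subjects. Precision falls further if age is collinear with group or dose. Frequency matching, if chosen, would slow HF recruitment.
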